## Design & Procedures

- Describe the study, providing details regarding the study intervention (drug, device, physical procedures, manipulation of the subject or the subject's environment, etc.). Discuss justifications for placebo control, discontinuation or delay of standard therapies, and washout periods if applicable. Identify procedures, tests and interventions performed exclusively for research purposes or more frequently than standard of care. Include alternative therapies, concurrent therapies discontinued per protocol, risk benefit ratio, and use of tissue/specimens. Discuss monitoring during washout periods if applicable. Include brief description of follow-up, if any.

**Research Plan and Design.** We will use a pilot RCT to examine PainPac feasibility (primary aim and outcome), patient burden, engagement, acceptability, and initial pain-related outcomes, compared to a therapist led videoconference delivered behavioral pain intervention (PCST-Video) in colorectal cancer patients with pain (N=60). We will use quantitative and qualitative data to optimize PainPac. Participants will complete assessments at pre-treatment (A1), post-treatment (A2; 4 weeks post-A1), and 1 month follow-up (A3; 1 month post-A2) (months 5-22). Assessment contents can be found in the attached document, Data Dictionary, and will be distributed to both study groups. These assessments contain items that will be used to assess Aim 2 for both study groups. The pain management strategies are relevant and efficacious across cancer types. Due to the pilot nature of this work, we will enroll an opportunity sample of colorectal cancer patients. [name] (PI) has tested behavioral symptom management protocols in colorectal cancer patients and has an established relationship with [name] (Co-I) and the GI cancer clinic teams, all of which allows for an efficient start up. Further, colorectal cancer is associated with significant pain, impacts men and women, and spans a large age range, making it a good population for this early work. The preliminary work for PainPac has been in cancer patients including breast, prostate, lung, and stem cell transplant patients. If PainPac is feasible and shows promise, this project will lead to effectiveness testing in diverse cancer patients.

**Participants and Recruitment.** Participants will include (N=60) colorectal cancer patients at the Duke Cancer Institute (DCI) that report pain  $\geq 4$  at a clinical oncology appointment. Standard care is to record a 0=no pain to 10=worst imaginable score at every clinic appointment and pain  $\geq 4$  represents clinically significant pain and allows for pre- to post clinically significant change. Patients' pain will be re-assessed at enrollment to confirm eligibility. Other eligibility criteria: 1)  $\geq 18$  years and 2) stage I-IV colorectal cancer diagnosis  $< 2$  years. Exclusion criteria: 1) cognitive impairment, 2) brain metastases, 3) severe psychiatric condition (e.g., psychosis) that would contraindicate safe participation, or 4) participation in behavioral pain management in the past 6 months.

**Recruitment (months 4-18).** [name], Deputy Director of DCI, and [name], oncologist and Co-I, will assist with recruitment. In 2021, there were 1,457 unique patients with colorectal cancer seen at DCI. This suggests more than adequate numbers to complete the proposed work. We will use our established screening procedures that use electronic medical records (EMR) to identify eligible patients and the same Duke IRB-approved, direct-to-patient recruitment method that has resulted in high rates of enrollment in our previous work. Under a HIPAA waiver, staff will use DEDUCE to query the Duke EMR and identify potential participants. After chart review to verify eligibility, staff will mail patients a study brochure and introductory letter. The letter includes a number to call if the patient is interested (or to opt out) and explains that a staff member will contact them soon. All patients who meet eligibility criteria will be contacted unless they opt out. If interested and eligible, patients will complete electronic consent. We have successfully recruited for many trials using this well-developed EMR-based system and remote, direct-to-patient approach.

**Randomization.** Following consent and baseline assessment, patients will be randomized with equal allocation to: 1) a mobile app behavioral cancer pain intervention (PainPac) or 2) a therapist led videoconference delivered behavioral cancer pain intervention (PCST-Video). For patients randomized to PainPac, eligibility will result in electronic push of study information to the patient through MyChart, email, and/or text, and research staff will confirm app download. All participants will continue to receive standard care from their medical team. No participant will be asked to change pain management strategies. Data from 2021 suggests the majority of Americans (85%) own a smartphone, and similar statistics are reported in cancer patients. Participants who do not have a smartphone will be loaned one with a data plan to access the PainPac app or PCST-Video sessions. Participants will receive instructions for PainPac or PCST-Video technology, handouts with FAQs and troubleshooting strategies, and contact information for the study team and tech support. Therapists and staff will check in with participants regarding technology usability and tech assistance will be available within 24 hours.

**PainPac.** PainPac is a patient-focused intervention developed using cognitive-behavioral theory and empirically supported strategies to enhance patients' ability to manage their pain. [name] (mentor to Drs. [name] and [name]) first developed and tested Pain Coping Skills Training (PCST) intervention protocols for patients with arthritis; he has conducted many trials demonstrating the efficacy of these protocols. Drs. [name] and [name] have applied their experiences working with [name] to work with cancer patients with pain, and have developed and tested PCST interventions for cancer patients and focused on making them more accessible. PainPac is a logical extension of this work and expected to be an efficacious and innovative option for a highly scalable, implementable, and efficacious behavioral pain management intervention for patients with cancer. PainPac is a mobile app available to patients on a smartphone or tablet. PainPac uses Social Cognitive Theory to promote behaviors to improve pain, self-efficacy for pain management, and pain-related quality of life indices. It also uses real-time data to personalize the intervention and messaging to participants. PainPac contains 4 modules, each including a skill that has shown efficacy for reducing pain in patients with cancer. The 4 skills modules are: 1) progressive muscle relaxation (PMR), 2) imagery relaxation, 3) activity rest cycling and pleasant activity planning, and 4) cognitive restructuring. Patients are prompted to complete one module each week for 4 weeks; each module requires patients to attend to content for 8 minutes and includes text, video, and audio presentation of skill rationale and expected outcomes, skill modeling and tips for daily use, and a patient story about skill use. The first 3 minutes include a rationale for the pain coping skill and expected outcomes of skill mastery and use delivered through audio with text on screen. The next 3 minutes include video with skill modeling and tips for use/practice. The final 2 minutes include a patient story about their experiences (challenges/benefits) with the skill. Each module has complementary content designed to lead to skills practice and mastery. For example, the PMR module has PMR audio clips for full (15min), medium (5min), and short (2min) practice. Importantly, the app also has interactive components to improve coping skills engagement. App messaging includes: 4/week coping messages encouraging practice; daily assessment of pain and skills use that informs personalized messaging to further promote engagement; reminders for skills practice / module completion. PainPac includes an engagement tool with rewards based on completion of modules, assessments, and skills practice. Pattern Health (Durham, NC) specializes in patient-centered apps for medical research with expertise in patient engagement. Pattern Health has a portfolio of funded work with NIH researchers and an established relationship with the study team and Duke, and will be contracted for this study.

**Videoconference Delivered Pain Coping Skills Training (PCST-Video).** Participants randomized to PCST- Video will receive 4 behavioral cancer pain intervention sessions delivered by videoconferencing by

a pain therapist in the medical center to the patient in their natural environment (e.g., home). Sessions will be scheduled weekly for 45-60 min and mimic in person sessions. In rare circumstances when the participant is not able to connect via videoconferencing, the PCST-Video sessions can be delivered via phone. This is a backup option that will rarely if ever be used due to extenuating circumstances. PCST-Video session content is based on Pain Coping Skills Training (PCST) designed by [name] (mentor to Drs. [name] and [name]) and matches the PainPac skills modules described above. PCST-Video participants will complete assessments at the same intervals as PainPac participants. Interventionist Training (months 2-4). PCST-Video will be delivered by a masters or doctoral level psychologist with experience delivering behavioral pain interventions. Drs. [name] and [name] will provide training and therapists will be certified (>90% ratings of competence and protocol adherence) to deliver the intervention. Therapists will follow a manualized protocol; treatment strategies will be taught through didactic instruction, audio-/video-recorded illustration from model cases, and role-play of common scenarios. Sessions will be recorded and reviewed in supervision by [name]. Procedures to Ensure Consistency of Treatment. 1) The therapist will follow a manual; 2) Weekly supervision will occur; 3) Session recordings will be reviewed and feedback provided; and 4) Ratings of treatment adherence and competence will be conducted. Treatment Adherence and Therapist Competence. Ratings of protocol adherence will be made by Drs. [name] and [name]. Protocol adherence criteria will be developed for each session with satisfactory adherence ≥90% on the rating scale. Ratings of therapists' competence will be used to evaluate 20% of PCST-Video sessions.

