**Statistical Design and Analyses.** A pilot trial (N=60) will be used to compare PainPac (n=30) to PCST-Video (n=30) on measures of feasibility (primary aim), burden, acceptability, engagement, and initial pain-related outcomes. Sample size was informed by pilot trial guidelines for RCTs of behavioral interventions,  and past similar studies, that suggest 30 participants per condition is sufficient for determining feasibility and acceptability, and feasibility of a future definitive trial. We anticipate no more than 25% attrition by 1 month post- baseline, based on previous psychosocial studies with cancer patients. Both groups of 30 participants are needed because we aim to demonstrate two types of feasibility: feasibility of the PainPac app, which only requires the 30 PainPac participants, and feasibility of the subsequent larger RCT (i.e., recruitment, assessments), which requires all 60 PainPac and PCST-Video participants. We are recruiting both sexes and all genders, and we expect a nearly equal sample size between sexes. To account for sex as biological variable, we will describe all outcomes disaggregated by sex. We will examine intervention effects and use this data to optimize PainPac. Aim 1. Feasibility (accrual, attrition, adherence), burden, acceptability, and engagement will be assessed post-treatment and descriptive statistics will be produced for PainPac and PCST-Video. Overall trial feasibility benchmarks include reaching target accrual (N=60) within 15 months and <25% attrition by 1 month post- baseline. Descriptive statistics will be used to report non-eligibility and refusal. Data of non-completers will be compared to completers. 75% completed will serve as our feasibility benchmark. If >25% of consented patients drop out, PainPac will not be considered feasible. We do not expect attrition to be greater in the PainPac condition compared to PCST-Video. PainPac feasibility benchmarks include protocol adherence indicated by calculating the degree to which participants are willing/able to complete study assessments (pre, post, follow- up) and the 4 PainPac skills modules or 4 PCST-Video sessions. 75% completed will serve as our benchmark. If >25% of consented patients do not complete the intervention (modules /sessions and assessments), PainPac will not be considered feasible. We expect adherence in the PainPac condition will be at least comparable to PCST-Video. Patient Burden will be measured as a continuous variable by assessing physical, emotional, and financial burden of engaging in the study intervention. We expect burden will not be greater in PainPac compared to PCST-Video. Patient Engagement will be assessed by electronic app data (e.g., PainPac weekly log-ins) and patient self-report defined as the

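### The post-treatment assessment (A2) is timed from a baseline taken before randomisation, so it can fall before the four-week intervention is finished

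*Combined protocol and SAP*

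**What the plan says.** All places are in the combined protocol and SAP.

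- **Design & Procedures, Research Plan and Design** (repeated under Subject Recruitment and Compensation): the second assessment is "post-treatment (A2; 4 weeks post-A1", and A3 is one month after A2.
- **Design & Procedures, Randomization**: "Following consent and baseline assessment, patients will be randomized with equal allocation". App download is then confirmed by staff, and participants without a smartphone are loaned one.
- **Design & Procedures, PainPac**: "Patients are prompted to complete one module each week for 4 weeks".
- **Design & Procedures, PCST-Video**: there are four sessions, and "Sessions will be scheduled weekly for 45-60 min". This arm is assessed at the same intervals as PainPac.
- **Data Analysis & Statistical Considerations**: feasibility, burden, acceptability and engagement "will be assessed post-treatment and descriptive statistics will be produced for PainPac and PCST-Video". One of the attrition benchmarks is read at one month after baseline. Pre-to-post values are described, and Cohen's d is reported at follow-up.

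The plan does not limit the interval from A1 to the first module or session. It gives no window for A2, and no rule for A2 when modules or sessions run late.

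**The concern.** The label and the clock do not match. A2 is meant to describe participants after treatment, but its date is counted from a point before allocation, and treatment of about the same length has to fit in between. Followed exactly, the rule can call for A2 while the fourth skill is still being learned or has not yet been delivered.

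The measures exposed are those read at A2: burden, satisfaction, engagement and the pre-to-post descriptions of pain outcomes. A participant rated before the fourth contact rates a partial intervention. A3 inherits the problem because it is counted from A2, so the true interval from end of treatment to follow-up will vary between participants. A pilot meant to inform the timing and outcome measures of a larger trial should not leave this open.

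**Working it through.** **Plan's own figure.** The plan has no calculation behind the four-week point. Its one computed design figure, more than 80% power at d = 0.74 with 30 per arm, reproduces (80.5% by two-sample t-test) and does not bear on timing. The check is day arithmetic.

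**Inputs from the plan.** A1 is day 0 and A2 is day 28. There are four contacts, one per week, in both arms, and randomisation comes after A1.

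**Inputs the plan does not give (assumed).** L is the number of days from A1 to the first module or session. q is the chance that each of contacts 2 to 4 slips by one week.

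**Step 1: contact dates with no slips.** Contacts fall on days L, L+7, L+14 and L+21. The fourth week ends on day L+28.

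| Lag L (days) | Fourth contact | Fourth contact against A2 (day 28) | End of fourth week |
|---|---|---|---|
| 0 | day 21 | 7 days before | day 28 |
| 3 | day 24 | 4 days before | day 31 |
| 7 | day 28 | same day | day 35 |
| 8 | day 29 | 1 day after | day 36 |
| 14 | day 35 | 7 days after | day 42 |

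**Step 2: slack.** The fourth contact is on or before A2 when L + 21 + (days slipped) ≤ 28, that is, when L + (days slipped) ≤ 7. Start-up and rescheduling share those 7 days. The full four-week programme ends by A2 only if L = 0.

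**Step 3: one slipped week.** The fourth contact moves to day L+28, which is after A2 for every L of 1 or more (L = 3 gives day 31).

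**Step 4: PainPac.** Module 4 belongs to days L+21 to L+28. With a lag of 1 to 7 days and no slip, A2 falls within that week. A participant starting on day 3 has had 28 − 24 = 4 of the 7 days of week 4.

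**Step 5: share with the fourth contact after A2.** With a lag of 1 to 7 days, one slip is enough, so the share is 1 − (1 − q)³.

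| Assumed q | Share | Of 30 in an arm |
|---|---|---|
| 0 | 0% | 0 |
| 5% | 14% | about 4 |
| 10% | 1 − 0.729 = 27% | about 8 |
| 20% | 49% | about 15 |
| 30% | 66% | about 20 |

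With a lag of 8 days or more, the fourth contact is after A2 for everyone, whatever q is. These shares illustrate sensitivity to the assumptions. They are not estimates for this trial.

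**The case against.** The strongest reply is that the schedule can work as written. Four weekly contacts span 21 days, not 28, so a participant who starts within a week and misses nothing has had all four by A2. A PainPac module has only 8 minutes of content, so one due on day 24 can readily be finished by day 28. This stands. It would be wrong to say that the schedule leaves no slack or that A2 always falls inside treatment.

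Three stronger readings are tempting, and the documents support none of them.

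- **PCST-Video is hit harder, which flatters PainPac.** The Background names scheduled appointments as a barrier, so the idea is plausible. But no lag or slip rate is given by arm. PainPac has its own start-up step, and loaned phones can delay either arm. If both programmes are counted to the end of week four, equal lags affect them equally. The direction cannot be established.
- **Sessions not yet due are scored as non-adherence.** At q = 10%, about 8 of 30 (26.7%) would exceed the plan's 25% limit if counting stopped at A2. But adherence as defined includes the follow-up assessment, and no day-28 cut-off is stated. What stands is that the cut-off is undefined.
- **The Aim 2 contrast is compromised.** Cohen's d is reported at follow-up. If that means A3, the main contrast comes a month after A2 and is affected less. The analysis is descriptive, with no hypothesis test.

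It is also fair to say that the slip rates are assumed, and that a slip need not cost a full week if sessions are made up sooner. Step 2 allows for shorter slips.

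**Conclusion.** The point holds in a limited form. The plan's own calendar allows at most 7 days for start-up and rescheduling combined. Any lag puts A2 before the four-week programme ends. A lag over 7 days, or a shorter non-zero lag plus one slipped week, puts it before the fourth contact. That much needs no outside data. The share of participants affected does, and the documents do not supply it. It could be 0%, and it is 27% under an assumed 10% weekly slip rate with a 1 to 7 day lag.

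The consequence is possible blurring of the A2 measures and uneven spacing of A3. It is not a demonstrated bias towards either arm. This is a cheap improvement rather than a fatal flaw, but it is more than missing detail, because a stated rule can, when followed, measure post-treatment outcomes before treatment is complete.

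**What to change.** 1. Time A2 from randomisation, with one target day and one window common to both arms, late enough for four weekly contacts plus start-up. At 5 weeks, 35 − 21 = 14 days are available for start-up and slips before the fourth contact; at 6 weeks, 42 − 21 = 21 days. Keep A3 one month after A2.
2. State one cut-off date for counting modules and sessions, the same in both arms.
3. Restate the attrition benchmark now read at one month after baseline (Data Analysis & Statistical Considerations) so that it matches the new A2. It is part of the primary aim, so make the change before outcome data are reviewed.
4. Report the time from last module or session to A2, by arm.

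The intervention schedule is untouched. The cost is protocol wording and date settings in the data-capture system. Recruitment ends in month 18 and assessments run to month 22. A 6-week A2 plus one month to A3 is about 2.5 months, so a participant randomised at the end of month 18 finishes around month 20.5. The downside is that participants who start at once and miss nothing wait 1 week (35 − 28 days) to 2 weeks (42 − 28 days) between the end of the fourth week and A2.

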## Selection of Subjects

- List inclusion/exclusion criteria and how subjects will be identified.

**Participants and Recruitment.** Participants will include (N=60) colorectal cancer patients at the Duke Cancer Institute (DCI) that report pain  $\geq 4$  at a clinical oncology appointment. Standard care is to record a 0=no pain to 10=worst imaginable score at every clinic appointment and pain  $\geq 4$  represents clinically significant pain and allows for pre- to post clinically significant change. Patients' pain will be re-assessed at enrollment to confirm eligibility. Other eligibility criteria: 1)  $\geq 18$  years and 2) stage I-IV colorectal cancer diagnosis  $<2$  years. Exclusion criteria: 1) cognitive impairment, 2) brain metastases, 3) severe psychiatric condition (e.g., psychosis) that would contraindicate safe participation, or 4) participation in behavioral pain management in the past 6 months.

*Recruitment (months 4-18).* [name], Deputy Director of DCI, and [name], oncologist and Co-I, will assist with recruitment. In 2021, there were 1,457 unique patients with colorectal cancer seen at DCI. This suggests more than adequate numbers to complete the proposed work. We will use our established screening procedures that use electronic medical records (EMR) to identify eligible patients and the same Duke IRB-approved, direct-to-patient recruitment method that has resulted in high rates of enrollment in our previous work. Under a HIPAA waiver, staff will use DEDUCE to query the Duke EMR and identify potential participants. After chart review to verify eligibility, staff will mail patients a study brochure and introductory letter. The letter includes a number to call if the patient is interested (or to opt out) and explains that a staff member will contact them soon. All patients who meet eligibility criteria will be contacted unless they opt out. If interested and eligible, patients will complete electronic consent. We have successfully recruited for many trials using this well-developed EMR-based system and remote, direct-to-patient approach.

## Subject Recruitment and Compensation

- Describe recruitment procedures, including who will introduce the study to potential subjects. Describe how you will ensure that subject selection is equitable and all relevant demographic groups have access to study participation (per 45 CFR 46.111(a) (3)). Include information about approximately how many DUHS subjects will be recruited. If subjects are to be compensated, provide specific prorated amounts to be provided for expenses such as travel and/or lost wages, and/or for inducement to participate.

We will use a pilot RCT to examine PainPac feasibility (primary aim), patient burden, engagement, acceptability, and initial pain-related outcomes, compared to a therapist led videoconference delivered behavioral pain intervention (PCST-Video), in patients with colorectal cancer and pain. This study will be conducted at the Duke Cancer Institute (DCI) and involve 60 colorectal cancer patients with pain. [name], Deputy Director of the Duke Cancer Institute, and [name], GI oncologist physician champion and Co-Investigator, will work closely with [name] and the study team to assist

with recruitment. Drs. [name] and [name] are committed to this work; [name] has a history of support from both Drs. [name] and [name], and has worked closely with [name] on past trials and successfully recruited cancer patients with pain. All recruitment procedures comply with HIPAA guidelines and will receive approval from the Duke University Health System (DUHS) institutional review board (IRB). During our most active phase of recruitment, we will recruit approximately 12-18 patients per quarter (4-6 patients/month) over the course of 15 months (N=60) of this two-year R21 project.

Patient participants will be recruited through our well-developed recruitment system that uses linked electronic medical records at Duke University Medical Center (DUMC) to identify patients who meet study criteria. We will use the same Duke IRB-approved, direct-to-patient recruitment method that has resulted in high rates of enrollment in our group's previous work, including PainPac preliminary work and trials with patients with colorectal cancer. Under a HIPAA waiver, study staff will use DEDUCE to query the Duke electronic medical records (EMR) and identify potential participants. After a careful chart review to verify initial eligibility (e.g.,  $\geq 18$  years, colorectal cancer diagnosis, stage I-IV, in the last 2 years), study staff will mail potential participants a study brochure and introductory letter signed by the PI. The letter will state that the patient may be eligible to participate in a research study evaluating a mobile app behavioral cancer pain intervention for patients with cancer and pain. The letter includes a number to call if the patient is interested in learning more about the study (or would like to opt out) and explains that a study staff member will contact them about the study. Patients will then be called by highly trained study staff to assess interest. All patients who meet eligibility criteria will be contacted *unless they opt out*. Consistent with Duke's direct-to-patient recruitment guidelines, we will only attempt to contact patients a maximum of three times if we are unable to reach them. If a patient is interested when contact is made with a study team member, they will be provided with information about the study, its purposes, requirements, and time commitment. Interested patients will complete a scripted telephone screening (e.g., BPI pain severity) compliant with DUHS IRB policies to confirm full eligibility. Those who do not pass the telephone screening but ask for resources will be provided with a list of free resources available through the Duke Cancer Patient Support Program (e.g., financial support, individual and couple counseling). Eligible patients who wish to enroll in the study will complete an electronic consent form; a member of the study team will provide private consent and answer any questions that the potential participant may have. Those who do not have access to the internet for completing the electronic consent form will be mailed a paper copy. This remote, direct-to-patient recruitment approach has allowed us to efficiently reach more patients while reducing numerous obstacles encountered with methods that require physician time and clinic resources. We have successfully recruited for many trials using this well-developed recruitment system.

Participants will complete assessments at pre-treatment (A1), post-treatment (A2; 4 weeks post-A1), and 1 month follow-up (A3; 1 month post-A2) (months 5-22). Participants will receive \$30 for each assessment (totaling up to \$90 for all 3).

